### **Compensation:**

Subjects will be compensated for each study visit (\$75 for the Screening Visit and Randomization Visit, and \$125 for Visit 3) and for the 1-week and 7-week phone calls (\$25 each). Subjects will receive a completion bonus when they have completed the study in its entirety (\$200 for the Final Visit).

[figure not shown]
See below for the **Study Flowchart** and **Table of Procedures**.

**Table of Procedures:**

Visit	Screening Period			Treatment Period			
	Pre-V1	V1/ Screening	V2/ Randomizat ion	Phone contact 1	V3/ Placebo non- responder re- randomization	Phone contact 2	V4/ Treatment End
Study Week	-4	-2	0	1	6	7	12
Visit Location	Phone	Office/ Phone	Office/ Phone	Phone	Office/Phone	Phone	Office/ Phone
General/ Screening Assessment	Sleep/medical/mental health phone screening and verbal consent	x					
	Written Informed Consent		x				
	Eligibility Criteria	x	x				
	Medical History & Physical Exam		x a				
	Urine hCG	x			x		
	Drug Panel Urinalysis	x					
	Concomitant Medication	x	x	x	x	x	x
	ISI	x	x		x		x
	PGI-I				x		x
	BDI		x		x		x
Vitals	DQOL		x		x		x
	Diabetes Distress Scale		x		x		x
Lab Tests	Height/Weight/Heart Rate/Blood Pressure		x a	x a		x a	x a
	HbA1c	x	x b		x		x
Sleep Assessment	CRP	x	x b		x		x
	Sleep Diaries (administer/review)	x c	x c		x d		x d
Medication Dispensing *by mail	PSQI		x		x		x
			x	x*	x	x*	
Safety Assessment/ Adverse Event Reporting				x	x	x	x
					x		x
Medication Adherence							

Conditional study procedure: a = only performed at in-person visit  
b = only performed if four weeks have passed between Screening and Randomization Visits  
Study procedures completed between study visits: c = daily for 2 wks following visit, d = daily for 2 wks prior to visit

### Study Flowchart:

## VI. STUDY MEDICATION AND SUPPLIES

### Study Treatments:

The study medication will consist of 10 mg or 20 mg suvorexant tablets, or matching placebo, prepared in identically appearing capsules by Merck and distributed by the MGH Clinical Trials Pharmacy. The medication will be titrated and distributed according to the following schedule:

### Dispensing Schedule:

**Double-Blind Topiramate / Placebo Dosing**

Week	Study Medication		
	Treatment	Placebo	Placebo Non-Responders
1	10 mg capsule	10 mg capsule	
2 - 5	10 or 20 mg capsule	10 or 20 mg capsule	
6	10 or 20 mg capsule	10 or 20 mg capsule	10 mg capsule
7-12	10 or 20 mg capsule	10 or 20 mg capsule	10 or 20 mg capsule

Subjects will be instructed to take the study medication within 30 minutes of going to bed, and will be informed during the consent process that they may be receiving drug or placebo at different points during the study. Participants will be instructed to take 10 mg nightly for the first 7 days. If the 10-mg dose is well tolerated but not effective after one week of treatment, as determined by the one-week phone visit, the dose can be increased to 20 mg. This will be repeated at the 6-week visit for placebo non-responders.

Subjects will taper off their study medication by taking 10 mg for 3 days after the Final Visit, if 20 mg was taken during the study.

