### **Study Design and projected enrollment:**

This is a parallel, two-arm, double-blind, randomized placebo-controlled 3-month trial using the sequential parallel comparison design (SPCD), investigating the effects of suvorexant 10–20 mg on subjective total sleep time in patients with suboptimally controlled Type 2 diabetes. The SPCD consists of two stages, with data being pooled from both stages. The first phase involves an unbalanced randomization between placebo and active treatment with more patients randomized to placebo. In the second phase, non-responders treated with placebo are re-randomized to either active treatment or placebo. The first stage is a standard parallel comparison design. However, this first stage generates a cohort of placebo non-responders who then enter the second stage where placebo responses will be lower. This design enriches the primary analysis population, reducing the impact of placebo response rates, and allowing trials to be conducted with reduced study sample size without corresponding decreases in statistical power.

All study procedures will be conducted at Massachusetts General Hospital. We expect to consent and evaluate for eligibility up to 120 Type 2 diabetics in order to achieve our projected randomized sample size of 72 patients with Type 2 diabetes. Subjects will be randomized in a 1:2 ratio to suvorexant 10–20 mg or equivalent placebo for six weeks followed by re-randomization of placebo non-responders to either suvorexant or placebo in a 1:1 design; this will allow 62 Type 2 diabetics to complete the trial at 3 months, after allowing for post-randomization drop-outs.

Eligible patients will be randomized to 6 weeks of suvorexant or placebo after an initial 2-week screening period and a two-week screening run-in period to ensure the stability of sleep disturbance. Participants will complete 4 study visits (consent/screening visit, randomization visit, a 6-week visit, and a 3-months-on-treatment visit). In addition, an initial telephone-based screening assessment and 2 interim phone visits (at 1 week and 7 weeks on treatment) will occur. Suvorexant will be started at 10 mg nightly for the first 7 days. If the 10-mg dose is well tolerated but not effective after one week of treatment, as determined by the one-week phone visits (at 1 week and 7 weeks of treatment for those originally randomized to suvorexant and placebo, respectively), the dose can be increased to 20 mg.

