### **RANDOMIZATION VISIT AND TREATMENT PERIOD:**

At the Randomization Visit, the 2-week sleep diary and laboratory results will be reviewed for definitive eligibility before the participant is randomized to treatment. Baseline subjective sleep measures will be determined from this 2-week period. Baseline questionnaires will be determined at the Randomization Visit; these questionnaires will be determined again at both the 6-week and 12-week visits. HbA1c and C-Reactive Protein tests will only be performed at the Randomization Visit if more than 4 weeks have elapsed between this visit and the Screening Visit. Baseline pre-treatment symptom measures will be determined at the Randomization Visit. Eligible participants will be randomized in a 2:1 ratio to 6 weeks of placebo or suvorexant. At their 6-week visit, placebo non-responders will be re-randomized to either suvorexant or placebo in a 1:1 ratio. The placebo non-responders will be determined by the unblinded research coordinator, who will review the 2 weeks of sleep diaries completed before the 6-week visit.

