#### **Study Medication Packaging:**

Medication will be prepared and packaged by the MGH Clinical Trials Pharmacy. The medication will be dispensed in bottles containing enough for 14 days of medication after the Randomization visit, then enough for weeks 2-5. After the 6-week visit, a 14-day supply will again be dispensed, following a supply sufficient for weeks 7-12. Bottles will be labeled with the patient name and ID and the dosing information. Bottles will be clearly labeled as containing either 10 mg or 20 mg matching placebo or suvorexant tablets.

Subjects will be dispensed the appropriate number of tablets needed until the next medication dispensing date. Study medication should be stored at room temperature 15-30°C (59-86°F), be protected from moisture, and be maintained in a secure area.

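### The dispensing table's week rows conflict with the 6-week re-randomization, the week-7 call and the prose beneath the table, leaving the first stage 2 week under two different dosing instructions

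*Combined protocol and SAP*

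**What the plan says.** Most of the document describes the same two-period schedule.

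- **Section IV, Study Design:** first-stage treatment runs "for six weeks followed by re-randomization of placebo non-responders to either suvorexant or placebo in a 1:1 design". The decision on a dose increase is tied to the week-1 call for those who start on suvorexant and to the week-7 call for those who start on placebo.
- **Section V, Randomization Visit and Treatment Period:** "At their 6-week visit, placebo non-responders will be re-randomized to either suvorexant or placebo in a 1:1 ratio".
- **Table of Procedures:** the clock reads "Study Week -4 -2 0 1 6 7 12". Randomization is at 0, the calls are at 1 and 7, re-randomization is at 6 and the end of treatment is at 12.
- **Section VIII, Key secondary and exploratory analyses:** effects are averaged over two periods of 6 weeks.
- **Section VI, prose under the dispensing table:** 10 mg for the first 7 days, with a possible increase after the one-week call. Then: "This will be repeated at the 6-week visit for placebo non-responders".

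The dispensing table in Section VI is headed "Double-Blind Topiramate / Placebo Dosing". Its rows are week 1, weeks 2-5, week 6 and weeks 7-12. The column for placebo non-responders is blank until week 6, where it shows 10 mg. It shows 10 or 20 mg for weeks 7-12.

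Study Medication Packaging uses the same labels. For stage 1 it describes "bottles containing enough for 14 days of medication after the Randomization visit, then enough for weeks 2-5". For stage 2: "After the 6-week visit, a 14-day supply will again be dispensed, following a supply sufficient for weeks 7-12".

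**The concern.** The table is more than an illustration. The Study Treatments paragraph in Section VI says the drug is titrated and distributed by the schedule that follows it, so a pharmacy or coordinator could reasonably work from the rows.

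The participants concerned have never taken suvorexant: earlier treatment with it is an exclusion criterion, and they have been on placebo throughout stage 1. For those re-randomized to suvorexant, the first week of stage 2 is their first exposure. For that week the prose gives one instruction and the table, read with consistent numbering, gives another. The heading's reference to a drug from outside this trial makes it harder to rely on the table without checking it.

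**Working it through.** **Inputs.** Row labels and cells: the dispensing table. Visit clock: the Table of Procedures. Meaning of week 1: the prose under the table, which gives 10 mg for the first 7 days, as the week 1 row does. Supply quantities: Study Medication Packaging. Visits are assumed to fall on their nominal dates, with day 1 as the first dosing day.

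**1. The stated design.** Stage 1 = 6 - 0 = 6 weeks. Stage 2 = 12 - 6 = 6 weeks. The calls fall 1 - 0 = 1 week and 7 - 6 = 1 week after the visit that opens each stage. So 6 + 6 weeks (42 + 42 days) is reproduced, and stage 2 begins on day 43.

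**2. The table under two single conventions.** Ordinal: week k = days 7(k - 1) + 1 to 7k. Elapsed: week k begins when k weeks have passed, so it covers days 7k + 1 to 7k + 7.

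| Row | Ordinal days | Elapsed days | Non-responder cell |
|---|---|---|---|
| 1 | 1-7 | 8-14 | blank |
| 2-5 | 8-35 | 15-42 | blank |
| 6 | 36-42 | 43-49 | 10 mg |
| 7-12 | 43-84 | 50-91 | 10 or 20 mg |

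- *Ordinal.* The non-responders' 10 mg row starts on day 36, a week before anyone can be in that column. Days 43-49, their actual first week of stage 2, fall in the 10 or 20 mg row, although the call that decides an increase comes at the end of that week.
- *Elapsed.* The 10 mg row lands correctly on days 43-49. But days 1-7 then have no row, and the last row ends on day 91, a week after the final visit at day 84.

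**3. A mixed convention.** Reading rows 1 and 2-5 as ordinal weeks and row 6 as the week that opens at the 6-week visit gives 1 + 4 = 5 weeks before that visit and 1 + 6 = 7 weeks after it (35 + 49 days). If the last row is taken as the interval between the week-7 and week-12 contacts, stage 2 is 1 + 5 = 6 weeks. The total is then 5 + 6 = 11 weeks, and days 36-42 have no row. Neither gives 6 + 6.

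**4. Where it matters.** The suvorexant and placebo columns show the same 10 or 20 mg entry in every row from week 2 on, so moving the week 6 row changes nothing there. The conflict is confined to the non-responder column.

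**5. Supply text by quantity.**
- Stage 1: 14 days + weeks 2-5 (4 x 7 = 28) = 42 days, against 42 needed.
- Stage 2: 14 days + weeks 7-12 (6 x 7 = 42) = 56 days, against 42 needed, a surplus of 14 days.

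The stage 2 sum treats the two supplies as additive, as in stage 1; the sentence is loosely worded and may intend otherwise. The repeated labels make it unlikely that the table's rows are an error of text extraction.

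**The case against.** The best defence is that rows 6 and 7-12 are visit weeks. Row 6 opens at the 6-week visit, and row 7-12 runs from the week-7 call to the final visit. The non-responder column then shows one week at 10 mg followed by 10 or 20 mg, as the prose says. Section IV also ties the increase to the week-7 call, so staff who read the whole protocol would probably not be misled. This is a plausible account of what was intended, and it limits the practical risk. It does not make the table correct: the convention has to change partway down, a week drops out, and no text says that the prose overrides the schedule Section VI points to.

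It is also fair to say that the packaging text does not place the stage 2 start in week 6. It names neither week 6 nor 10 mg for the second period, it dispenses the new supply after the 6-week visit, and its stage 1 quantity covers all 42 days. That stands. Its own fault is the 56-day total.

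A reader might go further and infer that stage 1 is cut to 35 days, or that stage 2 drug is taken during the diary nights that supply the 6-week outcome, contaminating the stage 1 placebo arm and biasing the primary contrast. The documents do not support this. Non-responders are identified by the unblinded coordinator, "who will review the 2 weeks of sleep diaries completed before the 6-week visit". Re-randomization takes place at that visit, and the second supply follows it. No route is described by which stage 2 drug could be taken on days 36-42.

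**Conclusion.** The dispensing table is wrong as written. No single week convention makes it agree with the visit schedule, the prose beneath it and two 6-week periods. Its size is a one-week offset in one column, which leaves the dose instruction for days 43-49 contradictory, together with a stage 2 supply description 14 days longer than the stage and a drug name that does not belong to this trial.

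This rests on week 1 meaning the first 7 days, as the prose and the week 1 row indicate, and on nominal visit timing. The 56-day figure also assumes that the two stage 2 supplies are additive. The finding shows neither a shortened stage 1 nor any effect on the primary estimate, and the documents give no basis for counting affected participants. The sample size is not involved. It deserves correction because it concerns first-week dosing of participants new to the drug and costs little to resolve.

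**What to change.** The sponsor should reconcile the table's week rows and the packaging text's supply weeks with the 6-week re-randomization, the week-7 call and the prose. Specifically:

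1. State one week-numbering convention, in days from the first dose, and use it in the dispensing table, the packaging text and the Table of Procedures.
2. State which dosing text applies to the first week after re-randomization, and make the table and prose agree. No dose or titration rule is proposed here.
3. State the intended supply for each stage so that the quantities match the stage lengths, or say that the excess is deliberate.
4. Correct the drug name in the table heading.

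The cost is a wording amendment to the protocol and to any pharmacy instructions drawn from it. No participants, visits, procedures or analyses are added.

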#### **Study Medication Packaging:**

Medication will be prepared and packaged by the MGH Clinical Trials Pharmacy. The medication will be dispensed in bottles containing enough for 14 days of medication after the Randomization visit, then enough for weeks 2-5. After the 6-week visit, a 14-day supply will again be dispensed, following a supply sufficient for weeks 7-12. Bottles will be labeled with the patient name and ID and the dosing information. Bottles will be clearly labeled as containing either 10 mg or 20 mg matching placebo or suvorexant tablets.

Subjects will be dispensed the appropriate number of tablets needed until the next medication dispensing date. Study medication should be stored at room temperature 15-30°C (59-86°F), be protected from moisture, and be maintained in a secure area.

#### **Study Medication Accountability and Compliance:**

Starting at the Randomization visit, study medication will be dispensed to each subject with instructions to return all unused medication and packaging (including empty bottles) at the next study visit in order to assess compliance. In the case of virtual study visits, participants will be required to show the study team over video how much medication is remaining. Returned study medication bottles may be re-dispensed to the same subject if appropriate. Additional bottles will be dispensed to each subject as needed.

All study medication dispensed by the investigator or designee will be accounted for throughout the study. Information about subject dosing and compliance will be recorded in the subject's study records. Subjects who are noncompliant with medications (according to pill counts and diaries) may be removed from the study at the discretion of the investigators.

The investigator agrees not to allow access to the study medication to any person except those named as sub-investigator(s) or clinical care staff, and dispense only to qualified subjects participating in the study.

**Randomization:**

Randomization will be used to avoid bias in the assignment of subjects to treatment, to increase the likelihood that known and unknown subject attributes (e.g., demographics and baseline characteristics) are evenly balanced across treatment groups, and to enhance the validity of statistical comparisons across treatment groups. Blinded treatment will be used to reduce potential bias during data collection and evaluation of clinical endpoints. An unblinded research coordinator will be responsible for all re-randomization determinations and communicating with the pharmacy in that regard.

At the Screening Visit, subjects will be assigned a 3-digit subject number, in ascending sequential order beginning with 001. The subject number will be retained by the subject for the duration of the study. The MGH Clinical Trials Pharmacy and unblinded research coordinator will provide and maintain randomization and blinding. Subjects will be randomized to receive either suvorexant or placebo in a 1:2 ratio, and placebo non-responders will be re-randomized to suvorexant or placebo in a 1:1 ratio at the 6-week visit. The re-randomization will be balanced by using permuted blocks of 4. Subject and investigator will be blinded to treatment assignment. Subjects will be randomized sequentially as they qualify for the study.

**Blinding:**

The randomization code will be maintained by the MGH Clinical Trials Pharmacy and will not be revealed to study subjects, investigators or blinded clinical staff until all subjects have completed and the database has been finalized.

Under normal circumstances, the blind should not be broken. The blind should be broken only if specific treatment would be dictated by knowing the treatment status of the subject. Individual code breaks by the investigator will normally result in withdrawal of the subject from the trial. The date, time and reason for the unblinding must be documented in the study files.

**VII. CONCOMITANT MEDICATIONS**

Concomitant medications will be assessed and recorded at each contact with study subjects (in-person and over the phone).

Rescue medications for the acute treatment or ongoing management of hyperglycemia will be based on the judgment of the participants' health care providers. Modification in the antidiabetic medication will be considered relevant if there is a 2-fold change in dosage for a hypoglycemic drug, a change of more than 10% in the dosage of insulin, or the addition or subtraction of an oral hypoglycemic agent or insulin. Relevant modifications will be recorded.

The following medications are considered exclusionary for this study, in addition to any medications not listed here but decided to be exclusionary by the Study Physician:

### **Exclusionary Medications**

- Strong inhibitors of CYP3A
  - Ketoconazole, itraconazole, posaconazole, clarithromycin, nefazodone, ritonavir, saquinavir, nelfinavir, indinavir, boceprevir, telaprevir, telithromycin, convivaptan
- \*Maximum dose of 10 mg will be considered for subjects taking moderate CYP3A inhibitors
  - Amprenavir, aprepitant, atazanavir, ciprofloxacin, diltiazem, erythromycin, fluconazole, fosamprenavir, grapefruit juice, imatinib, verapamil

### **Medication Side Effects and Adverse Events:**

The package insert for suvorexant includes warnings and precautions related to the following side effects or adverse events: sleepiness during the day, not thinking clearly; acting strangely, confused, or upset; “sleep-walking” or doing other activities during sleep, such as eating, talking, having sex, or driving a car; temporary weakness in your legs or inability to move or talk, cataplexy; and diarrhea, dry mouth, upper respiratory tract infection, headache, next-day drowsiness, dizziness, abnormal dreams, and cough.

Subjects will be informed of the risks associated with consuming alcohol while taking suvorexant, both at the time of consent and throughout the study. Subjects will be advised not to consume alcohol in combination with suvorexant due to additive psychomotor effects.

Subjects will be assessed for depression and suicidal ideation at each study visit, using the Beck Depression Inventory (BDI).

All adverse events that occur between the first study-related procedure and within 30 days of the last dose of study medication will be reported. Adverse events will be reported to the Partners IRB according to guidelines.

Subjects should report any adverse events voluntarily or in response to general, non-directed questioning (e.g., “How has your health been since the last visit?). For each adverse event reported by the subject, the investigator should obtain all the information required to complete documentation in the subject’s research file.

All adverse events, regardless of seriousness, severity, or presumed relationship to study therapy, must be recorded using medical terminology in the subject’s study documents. Whenever possible, diagnoses should be given when signs and symptoms are due to a common etiology (e.g., cough, runny nose, sneezing, sore throat, and head congestion should be reported as “upper respiratory infection”). The investigator must document his/her opinion concerning the relationship of the adverse event to the study medication. All measures required for adverse event management must be recorded in the source document.

### **VIII. STATISTICAL ANALYSIS**

Analysis of all study data will be conducted by [name] and [name], a statistician at Massachusetts General Hospital. All study personnel and participants will remain blinded to treatment assignment, including staff entering study data. Only the unblinded research coordinator, who will assess treatment response at 6-weeks, and the hospital Research Pharmacist who generates the randomization code will be unblinded to treatment assignment. The final database will not be unblinded until a medical and scientific review, protocol violators have been identified, and all study data are complete.

The sequential parallel comparison design was developed at Massachusetts General Hospital and has been used extensively in clinical trials funded by both industry and NIH. Experts at MGH in SPCD will be consultants in the statistical analyses of our data.

